# 2.9. STATISTICAL ANALYSIS

Quantitative variables will be expressed as mean and standard deviation (SD). Qualitative variables will be expressed as absolute (N) and relative (%) frequencies. Pearson's  $\chi^2$  test and Fisher's exact test (where it is necessary) will be used to compare proportions, as well as McNemar test will be used to compare the percentages of kinesiophobia between measurements. Student's t-test or nonparametric criterion Mann-Whitney will be used for the comparison of the quantitative variables between the two groups. The change in the used scales and other indicators of the participants over time will be tested using linear mixed models from which dependence coefficients ( $\beta$ ) and their Standard Errors (SE) will be obtained. The group, the measurement (endline vs baseline) and their interaction term (to be tested in which extent the change is different between measurements in the two groups), will be introduced as independent variables. In the cases, where the interaction term will be found significant, sex, age, BMI and the symptoms duration will be introduced in the model (the chosen confounding factors are the most significant), in order to be tested if the interaction remain significant. Moreover, in the case that measurements at some outcome measures will be found to differ significantly at the initial measurement between the two groups, a result not due to systematic error but found to be due to random sampling. In these cases, their initial values will be entered into the mixed linear models as an independent variable to ensure that the findings from the models are not due to the initial differences between the groups. In cases that will be found significant differences between baseline measurements, between the two groups, the initial measurements will be introduced in linear mixed models as independent variable, in order to be ensured that the findings from these models are not due to initial differences between the groups. All reported p values will be two-tailed and statistical significance will be set at p < 0.05. Analyses will be conducted using the IBM SPSS Statistics 26.0.

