# 2.4. OBJECTIVE GOALS

Objectives of the study are summarized in the investigation of statistically significant differences in the outcomes of interest, i.e. in the measurements for pain sensitivity, intensity and quality (pressure algometer and SFMPQ), functionality (NDI), ROM (Moover 3D Inertial Motion sensor), endurance of deep neck flexor muscles (Chattanooga Stabilizer Pressure Biofeedback), respiratory function (portable spirometer) and psychological parameters (HADS, TSK, FABQ, PCS, SF-12). Differences in the outcomes of interest may arise:

a) between the start time (baseline) and the end time of the study within the A-ATM group (A-ATM group at baseline versus A-ATM group after the intervention).

b) between the compared groups of the clinical trial {group A ATM (Intervention Group) versus group B A-S (Active Control Group)}, both at the beginning of the study, as well as after the intervention.

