# 2.5. MATERIAL AND METHOD

## 2.5.1. SAMPLE

## 2.5.1.1. SAMPLE CHARACTERISTICS

During the initial calculation of the sample number, the number of the participants was determined, with purpose, the method of Analysis of Variance (ANOVA) in two groups of equal population, to identify a standardized effect size equal to 0.25 with a power of 80% and a level of statistical significance of 5%. The standardized effect size is defined as follows: Let the measurement tool X and groups A, B and  $\mu$ A,  $\mu$ B

be the mean values of X in groups A and B. SD is the Standard Deviation of X in the whole population. The effect size is given by the formula  $(|\mu A-\mu B|)/SD$ . The calculation was performed with the program G\*power version 3.1.9.7\* and the necessary sample size was calculated at 126 subjects. According to the relevant literature, similar standardized sample sizes have been used in two studies dealing with chronic neck pain (Lundblad *et al.*, 1999; Malmgren-Olsson *et al.*, 2009). Moreover, a dropout rate of 20% was expected, so a final number of around 152 patients is realistic for this study.

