# 2.10. RESULTS

Through the research, the effectiveness or the ineffectiveness of the FM will be highlighted and comparisons will be made between the effect of FM and A-S, regarding specific parameters (outcome measures), that will be evaluated at specific times (before and after the completion of the intervention - five weeks). Findings will be drawn for each hypothesis of both research questions with the aim of verifying or rejecting them. In detail, pain sensitivity, cervical ROM, endurance of the deep neck flexor muscles, respiratory function, intensity and quality of pain, functionality and psychological factors will be assessed and contrasted between the two interventions. After comparing the mean values of the groups in each assessment for each outcome measure, it will be established on the first level if the method under consideration has benefits in patients with chronic neck pain. On the second level, it will be established if it shows statistically significant results compared to the A-S intervention, if non-significant differences are detected between the two groups or if the active control group predominates. The findings will be presented for each outcome measure separately.

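### No deciding test is named for the ATM versus A-S hypotheses; if either of two planned tests may decide, the 5% error could reach about 8–10%

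*Combined protocol and SAP*

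**What the plan says.** Section 2.9 gives two tools for comparing the arms on quantitative outcomes. The first is a two-sample test: "Student's t-test or nonparametric criterion Mann-Whitney will be used for the comparison of the quantitative variables between the two groups". The sentence names no time point and no rule for choosing between the two tests. The second is a model: "The change in the used scales and other indicators of the participants over time will be tested using linear mixed models", with group, measurement and "their interaction term (to be tested in which extent the change is different between measurements in the two groups" as terms. One level applies to everything: "All reported p values will be two-tailed and statistical significance will be set at p < 0.05".

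Two other sections bear on where the two-sample test is used. Section 2.4 makes statistically significant differences the objective and, in item (b), looks for them between the groups "both at the beginning of the study, as well as after the intervention". Section 2.10 says that findings will be drawn for every hypothesis of both research questions, and continues: "After comparing the mean values of the groups in each assessment for each outcome measure, it will be established on the first level" whether the method has benefits. A second level then covers the comparison with A-S.

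Section 2.5.1.1 bases the sample size on "the method of Analysis of Variance (ANOVA) in two groups of equal population". It does not say whether the means are five-week values or changes.

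**The concern.** The between-group hypotheses H0B1 to H0B11 in section 2.3 each need one test that accepts or rejects them. The plan contains two candidates. A comparison of group means after treatment and a comparison of changes from baseline are different statistics, and they can fall on opposite sides of p = 0.05 in the same data set. No sentence ranks them or says what follows when they disagree.

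This affects the main between-group hypothesis, H0B1 on pressure pain threshold, as well as the secondary ones. If the choice can be made after the results are seen, the stated 5% level is not protected, and discordant results would support either conclusion about ATM against A-S. The stated power is also not tied to either test.

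**Working it through.** **Inputs from the documents.** Two-sided 0.05 for every p value (section 2.9); 126 evaluable patients, hence 63 per arm, and 152 enrolled, hence 76 per arm (sections 2.5.1.1 and 2.5.1.2).

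**Assumed input.** The correlation ρ between a patient's baseline and five-week values is not given. It is varied from 0 to 0.95. Equal variances at the two measurements and complete data are also assumed. With two measurements and complete data, the interaction test amounts to a t-test on change scores.

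**Step 1: the plan's own figure.** With one deciding test the error is 5%. In 100,000 simulated trials per setting with no true difference (ρ = 0.3, 0.5, 0.7, 0.9; 63 or 76 per arm), the five-week t-test alone rejected in 4.9–5.1% and the change test alone in 4.9–5.2%.

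**Step 2: how closely the two tests are related.** Let Y0 and Y1 be the baseline and five-week values with common variance σ². Then Cov(Y1, Y1 − Y0) = σ²(1 − ρ), Var(Y1) = σ² and Var(Y1 − Y0) = 2σ²(1 − ρ). The correlation of the two test statistics is therefore

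r = (1 − ρ) / √(2(1 − ρ)) = √((1 − ρ)/2).

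At ρ = 0.5 this is √0.25 = 0.5.

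**Step 3: error if either test may decide.** This is the bivariate normal probability that |Z1| > 1.96 or |Z2| > 1.96 with correlation r:

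| ρ (assumed) | r | Either test significant | Simulation, 63 per arm | Simulation, 76 per arm |
|---|---|---|---|---|
| 0 | 0.707 | 8.3% | – | – |
| 0.3 | 0.592 | 8.8% | 8.8% | 8.7% |
| 0.5 | 0.500 | 9.1% | 9.1% | 9.2% |
| 0.7 | 0.387 | 9.35% | 9.2% | 9.3% |
| 0.9 | 0.224 | 9.6% | 9.6% | 9.7% |
| 0.95 | 0.158 | 9.7% | – | – |

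The ceiling, for two independent tests, is 1 − 0.95² = 9.75%. As a cross-check at ρ = 0.5, the either-test rate equals 5% + 5% minus the rate at which both reject. The simulated rate for both was 0.9%, and 10% − 0.9% = 9.1%.

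**Step 4: Mann-Whitney.** Using Mann-Whitney for the five-week comparison (20,000 trials, 63 per arm) gives 9.1% at ρ = 0.5 and 9.5% at ρ = 0.7. A free choice among t-test, Mann-Whitney and interaction gives 9.9% and 10.5%.

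**Step 5: does the covariate step protect the level?** Section 2.9 re-tests a significant interaction with sex, age, BMI and symptom duration added. This touches only the interaction route. In a fitted example with complete data, adding a patient-level covariate left the interaction estimate (0.472) and its standard error (0.159) unchanged. Adding baseline as a covariate to the same two-measurement model left the estimate at 0.472 and moved the standard error only to 0.153.

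**The case against.** The strongest reply is that the plan already points to the interaction. The H0B hypotheses are worded as effects on reduction or improvement, which means change. Section 2.9 states that the interaction is there to test whether change differs between the arms, and only the mixed models receive follow-up steps. Section 2.9 also needs a between-group test at baseline, to find outcomes that differ at the start, and the t-test or Mann-Whitney sentence may serve only that purpose. Item (b) of section 2.4 says where differences may arise and names no test.

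Much of this stands. The five-week use of the two-sample test is inferred from sections 2.4 and 2.10, not stated in the sentence that introduces it. No text says that significance on either test rejects H0B. What does not follow is that the matter is settled. Section 2.4 makes significant differences after the intervention an objective, section 2.10 draws its findings after comparing group means at each assessment, and nothing confines the two-sample test to baseline.

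A reader might also infer three stronger points that the documents do not support:

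- That section 2.10 reads the benefit of ATM from its contrast with the active control. Its two levels can be read as Research question 1 (before and after within ATM) followed by Research question 2, so the sentence needs clarifying, not deleting.
- That the trial was sized for the five-week comparison. Section 2.5.1.1 names group means and no time point.
- That the McNemar test on kinesiophobia is another route to H0B8. It compares measurements, not arms.

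**Conclusion.** The gap is real: two significance tests of the same between-group hypotheses are written into the plan, and none is named as deciding. Accepting either would raise the two-sided error per hypothesis from 5% to between 8.3% and 9.7%. The result depends little on the unknown correlation. It rests on equal variances at the two measurements, complete data and a two-test choice; letting the t-test and Mann-Whitney compete as well adds a little more.

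A reader might infer that the trial's actual error rate is about 9%. The documents do not support that. The figure is conditional on an either-test rule that the plan never states, and the rate is 5% if the interaction alone decides. No power or disagreement figure is attached here, because it would require choosing an effect size and a test that section 2.5.1.1 does not pin down.

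**What to change.** - **Section 2.9.** Name one five-week model contrast as the only test that decides H0B1 to H0B11: the group-by-measurement interaction or, preferably, its baseline-adjusted form. If the adjusted form is chosen, write the model out, with the five-week value as response and baseline as covariate for every outcome, because adding baseline to the two-measurement model leaves the estimate where it was. State that the five-week t-test and Mann-Whitney comparisons are descriptive.
- **Section 2.10.** Reword so that the first level refers to the before/after change in the ATM group (Research question 1) and the second level to the named contrast (Research question 2).
- **Section 2.5.1.1.** State which test the power refers to.

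The cost is a few sentences in three sections and no change to data collection. The downside is fewer p values to report.

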The demographic characteristics form includes information regarding the participant's gender, age range, body measurements (weight, height), educational level, employment status, and field of employment. In addition, it contains information on marital status, duration of symptoms, medication, and the presence of other medical condition, except for chronic non-specific neck pain. Regarding medication as well as the presence of another medical condition, they refer to drugs and diseases that are not included in the exclusion criteria.

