#### 2.5.3. OUTCOME MEASURES

Primary outcome measures will be the sensitivity of pain and secondary outcome measures will be the ROM of flexion, flexion-extension and lateral flexion of the cervical spine, the endurance of the deep flexor muscles of the cervical spine, the respiratory function, the intensity as well as the sensory and affective dimensions of the pain, the functional capacity of the neck, the anxiety and depression, the fear of movement, the perception of fear and the attempt to avoid pain in relation to physical and work activities, the degree of destructive views about pain, the quality of life and patients' perceived change in their health conditions. Furthermore, the compliance rate will be recorded.

The measuring tools were selected based on their validity, reliability, ease of application and clinical economy. The outcome measures were assessed before the start as well as at the completion of the therapeutic interventions at five weeks, for both groups.

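### The covariate check runs only after a significant group × measurement interaction and, read as main effects, cannot alter that interaction in patients with both measurements

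*Combined protocol and SAP*

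**What the plan says.** Section 2.9 says that change over time "will be tested using linear mixed models from which dependence coefficients" and standard errors are obtained. The model terms are given as "The group, the measurement (endline vs baseline) and their interaction term". Covariates come in at a second step: "In the cases, where the interaction term will be found significant, sex, age, BMI and the symptoms duration will be introduced in the model", "in order to be tested if the interaction remain significant". The threshold is stated once for everything: "All reported p values will be two-tailed and statistical significance will be set at p < 0.05".

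The section describes the four factors as confounders. It does not say in what form they enter, which covariance structure is used, or whether patients with only one measurement stay in the model. A separate step, which enters initial values when the groups differ at baseline, is not the subject of this point.

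Section 2.5.1.7 shows where the factors come from: a single demographic form that records gender, "age range, body measurements (weight, height), educational level" and, further on, duration of symptoms. Section 2.5.3 gives two assessment times: "The outcome measures were assessed before the start as well as at the completion of the therapeutic interventions at five weeks". Section 2.8 adds a four-month follow-up and Section 2.11 says there is none. The model in Section 2.9 has two measurement levels either way.

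**The concern.** The step has two weaknesses.

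First, it depends on the result. An outcome gets an adjusted estimate only if its interaction is already below 0.05. Eleven between-group hypotheses are listed in Section 2.3, and Section 2.10 promises findings for each, yet the outcomes would be analysed unequally. A difference obscured by chance imbalance would never be re-examined.

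Second, the step does not do what it is for. A factor measured once per patient, entered as a main effect, moves both of that patient's values by the same amount. The interaction compares change within patients, so the factor drops out. A report that a result stayed significant after adjustment for sex, age, BMI and symptom duration would read as evidence of robustness while carrying little or no information.

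**Working it through.** The plan states no figure for this check, so there is none to reproduce. The simulations use N = 152, the target in Section 2.5.1.1 (126 × 1.2 = 151.2, given there as around 152). How 126 itself was obtained is a separate matter and does not enter here.

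**Algebra.** For patient i at measurement t (0 = baseline, 1 = five weeks), with group g and patient-constant factors z:

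y(i,t) = b0 + b1·g + b2·t + b3·g·t + c·z + u(i) + e(i,t)

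The within-patient change is

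y(i,1) − y(i,0) = b2 + b3·g + e(i,1) − e(i,0)

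The terms c·z and u(i) have gone. With complete pairs, the estimate of b3 is the difference between groups in mean change, with or without z. A factor × measurement term k·z·t would leave k·z in the change and could move b3. A patient with only a baseline value contributes no change score, but does inform the between-patient part of the fit, where c·z remains. That is the only route by which main effects can move b3.

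**Simulation.** Random-intercept REML model, 3,000 trials per row. Assumptions not in the documents: intraclass correlation 0.6; covariates explain 30% of between-patient variance; true effect 0 or 0.35 SD; covariate effect on change 0 or 0.5 SD.

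Complete pairs:

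| True effect | Covariate effect on change | Significant unadjusted | Lost, main effects | Lost, factor × measurement | Gained, factor × measurement |
|---|---|---|---|---|---|
| 0 | 0 | 154 | 0 | 13.6% | 1.0% |
| 0 | 0.5 | 159 | 0 | 47.8% | 2.4% |
| 0.35 | 0 | 2,012 | 0 | 3.5% | 5.6% |
| 0.35 | 0.5 | 1,607 | 0 | 6.8% | 31.4% |

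Lost is the share of significant interactions that became non-significant; gained is the share of non-significant ones that became significant. In total 154 + 159 + 2,012 + 1,607 = 3,932 significant interactions, none lost with main effects. The estimate never moved by more than 1e-15, nor the p value by more than 1e-8.

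20% random dropout at five weeks, baseline-only patients kept, main effects:

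| True effect | Covariate effect on change | Lost | Median shift (SD) | Mean SE |
|---|---|---|---|---|
| 0 | 0 | 16/154 = 10.4% | 0.011 | 0.159 |
| 0 | 0.5 | 37/167 = 22.2% | 0.018 | 0.181 |
| 0.35 | 0 | 38/1,769 = 2.1% | 0.010 | 0.159 |
| 0.35 | 0.5 | 64/1,434 = 4.5% | 0.019 | 0.182 |

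With dropout assumed to differ strongly by arm and to depend on baseline and a covariate, the median shift was 0.045 to 0.057 SD and the share lost ran from 0% (0/1,298) to 35% (284/802). If only completers are analysed, the complete-pairs result applies again.

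**Cross-checks.** In one complete data set fitted with separate software, the interaction was 0.4517 (SE 0.1889) with and without the main effects, and 0.4602 (SE 0.1820) with factor × measurement terms. With 30 of the 152 five-week values removed, it went from 0.3288 to 0.3398 with main effects. In 30 complete data sets (63 per arm) with an unstructured covariance, main effects moved the estimate by less than 1e-14, while factor × measurement terms moved it by up to 0.38. The unstated covariance structure therefore does not rescue the check.

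**The case against.** A reader might infer that the check can never fail and that every significant result must pass it. The documents do not support that. Section 2.5.1.1 expects 20% dropout, and Section 2.9 names a mixed model without excluding patients who have one measurement. If they are kept, the estimate can move and a borderline p value can cross 0.05. This stands, and limits the claim to patients with both measurements. It does not make the check useful: the movement comes from incomplete pairs, and in complete pairs a factor that drives change still goes unaddressed.

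The form of entry is also unstated. Main effects is the literal reading, since the only interaction named is group × measurement. If factor × measurement terms were intended, the plan has to say so, and the same edit is needed.

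A reader might also infer that simple randomisation leaves the comparison confounded by these factors. It does not. Randomisation balances them in expectation, and the unadjusted test already allows for chance imbalance; simple randomisation merely does not force balance in this sample. Nor does the trigger inflate the type I error rate, because a check run only after significance can withdraw a claim but not add one.

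Finally, adjusting every outcome without naming a deciding model would give two p values per hypothesis. That is right, and the fix must deal with it.

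**Conclusion.** The point holds in a limited form. That the check depends on significance is plain from Section 2.9 and needs no modelling assumption. That main effects cannot alter the interaction in patients with both measurements is exact algebra, given the literal reading of how the factors enter. Through incomplete pairs the interaction can move, usually slightly under random dropout and more if dropout differs strongly by arm. The percentages rest on the assumed correlation, covariate effects and dropout pattern, and show a range rather than a forecast.

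The randomised comparison itself stands. What the plan forgoes is a robustness check that means something, the precision available from data already collected, and equal treatment of outcomes. This should be changed, but it does not threaten the validity of the main test.

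**What to change.** Delete the significance trigger. For every outcome, whatever its p value, pre-specify one adjusted model in which the factors can act on change. A suitable one regresses the five-week value on group, baseline value, sex, age, BMI and symptom duration. Section 2.5.1.7 records age as a band, so state that it enters as an ordered score or band midpoint. State in advance whether this model or the unadjusted interaction decides each hypothesis, and report the other as a sensitivity analysis. Say also how patients without a five-week value are handled, since this regression does not use them unless their values are imputed.

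The cost is a change of wording and one extra model per outcome, with every variable already on the demographic form. The model spends about five degrees of freedom (baseline value plus four factors), and more if age bands are entered as categories.

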## 2.5.1.2. METHOD OF RANDOMIZATION AND BLINDING

The sample will include 152 patients of both sexes and age range 19-70 years. Participants will be collected using the simple random sampling method and these meeting the inclusion and exclusion criteria will be recruited and will form the study sample. The participants will be allocated using the method of simple randomization with an allocation ratio of 1:1, i.e. in two equal groups of 76 people, each.

The randomization of patients to the A ATM group and the B A-S group will be performed with the help of a random number generator created in Stata software with the help of the "randomizer" package. The "randomizer" package through the principles of binomial distribution, randomly assigns to each participant their participation in either the intervention group or the active control group. In this way each participant will be placed in one of two groups at the start of the study and will remain in the same group for the duration of the study. The ratio of subjects between the two groups will be maintained at 1:1 throughout the study.

This study is a single blind clinical trial. The intervention will be perceived by the principal researcher, who will apply the treatment protocol in the intervention group (A ATM), the physiotherapist, who will apply the treatment protocol in the active control group (B A-S) and the participants. It is not feasible for both participants and therapists to be blinded, due to the nature of each intervention. All evaluations of the effectiveness of the treatment interventions will be carried out by two independent assessors who, although belonging to the research team of the study, do not know the type of intervention that each patient will receive, as well as the allocation of patients to the different treatment intervention groups (Kang, 2013, Opara *et al.*,

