# 2.5.3.2.11. CHANGE OF HEALTH CONDITION (GLOBAL PERCEIVED EFFECT / GPE)

The Global Perceived Effect (GPE) scale will rate the perceived change of the subject's health condition. It asks the patient to rate how much their condition has worsened or improved relatively to another predetermined point in time (Evans *et al.*, 2014). It is a numerical scale which consists of only one question with 5 possible answers. This scale is often used in musculoskeletal conditions, especially when they are chronic, such as chronic neck pain (Meisingset *et al.*, 2018). Despite the ease of application of the GPE, it is a challenge for patients to accurately remember the state in which they were recently and not to confuse the current state with the corresponding past state (Kamper *et al.*, 2010).

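### Adding the initial value to the mixed model as a main effect does not adjust the group-by-measurement interaction, so the promised protection against baseline differences is not delivered

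*Combined protocol and SAP*

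**What the plan says.** Section 2.9 analyses change over time with linear mixed models. The predictors are "The group, the measurement (endline vs baseline) and their interaction term", so each patient's baseline value is itself a response row and the interaction is the test of different change between groups.

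Two conditional steps follow.
- Step (a): "In the cases, where the interaction term will be found significant, sex, age, BMI and the symptoms duration will be introduced in the model", to see whether the interaction stays significant.
- Step (b): where the groups differ significantly at baseline, "the initial measurements will be introduced in linear mixed models as independent variable". The stated purpose is "to ensure that the findings from the models are not due to the initial differences between the groups". The instruction appears twice in similar words, and neither version mentions an interaction between the initial value and measurement.

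No covariance structure is given. Section 2.4 also asks for the change "between the start time (baseline) and the end time of the study within the A-ATM group". Section 2.5.1.2 states: "The participants will be allocated using the method of simple randomization with an allocation ratio of 1:1".

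**The concern.** The initial value is a fixed characteristic of the patient. As a main effect it shifts that patient's baseline and endline rows equally, so it cannot alter a contrast built on endline minus baseline. A chance imbalance does bias that contrast, through regression to the mean: the arm that starts lower tends to rise more. For pressure pain threshold, the more sensitive arm would appear to gain more.

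Step (b) exists to deal with exactly this case. On the plain reading it leaves the bias in place, while the report could say that initial differences had been dealt with. Simple randomisation does not balance baseline values by design, so correction depends on the analysis. The covariates in step (a), entered as main effects, cancel in the same way, so passing that step says little about confounding.

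**Working it through.** **Inputs.** From the documents: 152 patients, 76 per arm (2.5.1.2); "a dropout rate of 20% was expected" (2.5.1.1); two-sided 5% tests (2.9). With 20% loss, 76 × 0.8 = 60.8, about 61 complete pairs per arm. The plan gives no figure for the adjustment step, so there is none to reproduce. The pre-post correlation r is not in the documents; r = 0.4, 0.6 and 0.8 are assumed, with equal variances at both times and no true effect.

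**1. The estimate cannot move.** Write a patient's rows as Y0 and Y1. Adding b × Y0 to both leaves Y1 − Y0 free of b. With complete pairs the interaction equals the difference in mean change, with or without the term. Generalised least squares under 200 random 2×2 covariances agreed to within 3e-13. One fitted example (63 per arm, r = 0.5) gave −0.3816 both with and without the baseline term, against −0.0957 for ANCOVA.

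**2. Size of the remaining bias.** Under the null, the expected interaction given a baseline difference D0 is r × D0 − D0 = −(1 − r) × D0. The mean of |Z| given |Z| > 1.96 is 2 × 0.0584 / 0.05 ≈ 2.34. At 61 per arm, SE(D0) = sqrt(2/61) = 0.181 SD, so mean |D0| ≈ 0.42 SD. Multiplying by 0.6, 0.4 and 0.2 gives about 0.25, 0.17 and 0.08 SD, which the simulation below confirms.

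**3. The SE depends on the unstated covariance.** After step (b) the pooled slope is (1 + r)/2, and the covariance of the two residuals is −(1 − r)²/4, which is negative.
- A random intercept cannot fit a negative covariance, so its variance goes to zero. The SE shrinks by sqrt((3 + r)/4) = 0.922, 0.949, 0.975.
- Compound symmetry allowing negative correlation leaves the SE unchanged.
- An unstructured covariance has no maximum, because the baseline row is predicted perfectly. The log-likelihood was 100, 297, 578, 859 and 1139 at baseline coefficients 0.5, 0.9, 0.99, 0.999 and 0.9999.

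**4. Null simulation.** Complete pairs: 400,000 trials per r. Dropout: 20,000 per r (ANCOVA 4,000). All rows except the two marked overall are conditional on a significant baseline difference.

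| | r = 0.4 | r = 0.6 | r = 0.8 |
|---|---|---|---|
| *Complete pairs, 61 per arm* | | | |
| Bias, before and after (SD) | 0.252 | 0.167 | 0.085 |
| Rejects before step (b) | 21.3% | 15.6% | 10.5% |
| After, random intercept | 26.8% | 18.7% | 11.6% |
| ANCOVA | 4.9% | 5.1% | 5.0% |
| Common-baseline model | 5.3% | 5.7% | 5.5% |
| Overall two-step error | 5.3% | 5.1% | 5.1% |
| *20% random dropout, 76 per arm* | | | |
| Bias, before and after (SD) | 0.223 | 0.156 | 0.075 |
| Rejects before step (b) | 18.7% | 13.8% | 9.4% |
| After, random intercept | 28.0% | 20.8% | 13.9% |
| After, compound symmetry | 23.9% | 18.7% | 13.2% |
| ANCOVA | 4.7% | 5.1% | 5.1% |
| Overall two-step error | 5.6% | 5.5% | 5.3% |

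If dropout is related to baseline in opposite directions by arm (assumed log-odds of 1 per SD), step (b) adds a new shift of 0.12, 0.08 or 0.04 SD. It lowers the imbalance bias only from 0.23, 0.15, 0.08 to 0.21, 0.14, 0.07 SD.

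**5. Within-ATM change.** One arm carries half the imbalance. The bias is 0.126, 0.083, 0.042 SD and the paired test rejects in 12.7, 10.4, 7.7% of triggered trials. A common baseline gives 5.0, 5.4, 5.5%.

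**6. Step (a).** Four covariates, one correlated 0.4 with the outcome, and a true effect of 0.3 SD (all assumed). With complete pairs the shift is zero and the SE ratio is 1. With 20% random dropout the shift is 0.018, 0.012, 0.006 SD, and 968 of 1017, 1342 of 1380 and 2233 of 2252 significant results are kept.

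**7. Triggers.** Eleven between-group hypotheses at 5% give 11 × 0.05 = 0.55 expected triggers per trial. If independent, the chance of at least one is 1 − 0.95^11 = 43%.

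**The case against.** **The wording is loose.** The authors may have meant an initial-value-by-measurement term or an endline ANCOVA. Either removes the bias (at most 0.004 SD with the interaction term). That is a fair limit on the claim, but section 2.9 names an interaction where it wants one and names none here. The interaction reading is not clean either: with a random intercept and 20% random dropout it rejects in about 8% of triggered trials.

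**The overall effect is small.** This stands. The change contrast is unbiased over all randomisations. The excess over ANCOVA is 0.05 × (0.268 − 0.049) = 1.1% of null trials at r = 0.4 and 0.05 × (0.116 − 0.050) = 0.3% at r = 0.8.

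**r may be high.** The documents cite reliability coefficients of 0.84 to 0.93 for the algometer at the suboccipital region and 0.93 for the NDI, but 0.63 (intra-rater) for the craniocervical flexion test. These are ceilings for a five-week correlation under treatment, not estimates of it. If r is near 0.8 the bias is below 0.1 SD.

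**The baseline test would use all 76 per arm.** With complete data at 76 per arm the rejection rates are similar and the bias is 0.23, 0.15, 0.08 SD.

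**Smaller points that stand.** The promise concerns differences between groups, so the within-ATM bias is a consequence and not a broken promise. Step (a) creates no false positives with complete pairs. The count of 0.55 triggers is a minimum, because pressure pain threshold has several sites and some scales have subscales. Baseline means would be reported, so readers could see an imbalance, but seeing it does not correct the estimate.

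**Conclusion.** The concern holds on the main-effect reading, and it should be fixed. For complete pairs the invariance of the estimate is exact and depends on no assumption about r or the common covariance structure. With random dropout the average bias is also unchanged.

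The harm is conditional. Overall error stays at about 5.1 to 5.6%, but where step (b) is triggered the false-positive rate is roughly 10 to 28%, depending on the assumed r, the covariance structure and random dropout. With a random intercept the step makes it worse. For scale, section 2.5.1.1 defines its target as a standardised difference of 0.25, and the bias reaches that size at r = 0.4. The stated 126 patients correspond to a difference of 0.5 SD, and the bias is half of that. The magnitudes rest on the assumed r and equal variances; the direction does not change for any r below 1.

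**What to change.** - For every quantitative outcome measured at baseline and endline, prespecify one longitudinal model with a common baseline mean for the two groups and a stated covariance structure. It gives both the between-group effect and the within-ATM change.
- Endline ANCOVA on the outcome's own baseline would serve equally well for the between-group test. The within-ATM change would then need its own prespecified test.
- Delete the baseline significance test as a trigger.
- If sex, age, BMI and symptom duration are wanted, include them for all outcomes whatever the result, with measurement interactions in the longitudinal model.
- State that the Global Perceived Effect, which asks "how much their condition has worsened or improved relatively to another predetermined point in time" and so has no baseline value, is compared directly between groups. Section 2.9 already has suitable tests but does not name this outcome.

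The cost is a little more SAP text and analysis work. All variables are already collected, and no patients, visits or measurements are added.
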